subjects/parents/ guardians at the bedside, who meet the inclusion/exclusion criteria, with a brief explanation of the study. A more detailed explanation will be offered in a private room to those interested in participation. The alternative to participation is “not to participate”. Care will not be altered for patients who do not participate. Informed consent will be obtained if the patient and/or parent/legal guardian agrees to participate. Parents/legal guardians will be allowed an indefinite amount of time for questions and participation consideration. Parents/legal guardian will provide consent for 0-18 year old children (documented in writing using the PHRC approved consent form). The permission of both parents is required unless one parent is deceased, unknown, incompetent, or not reasonably available or if only one parent has legal responsibility for the care and custody of the child. Any child 14 years or older, who is able, will consent along with parent/guardian. The assent of each child (age 7 and older) who is capable of providing assent based on medical condition, age, maturity, and psychological state will be sought. According to a power analysis calculation, 75 children will be included in this study.

B. Treatment Assignment and Randomization

This is a randomized, double-blind, placebo-controlled trial. Patients will be randomly assigned to receive Selenium supplementation (either 2, or 4 ug/kg/day) or a placebo. 25 subjects will be in each group (total of 75 subjects). Randomization will occur by using a computerized randomization list. A pharmacist, who is not a member of the study staff, will prepare the supplements and label them accordingly prior to distribution.

V. Study Procedures

A. Study Parameters

- B. Lab studies conducted solely for the purpose of this study include plasma and urinary Se, plasma Gpx and dietary Se intake. Other parameters that will be included are demographics, medications, wound debridement procedures, invasive devices, mode of nutrition support, kilocalorie and protein intake, weekly weights, neurological status (as routinely assessed by the clinical team) and routine laboratory studies.

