where $Z_{(1-\alpha/2)}$ and $Z_{(1-\beta)}$ represent percentage points of the normal distribution for statistical significance level and power, respectively. The values used were 1.96 for a significance level of 5% and 0.8416 for a power of 80%. The Δ represents the standardized difference (the treatment difference divided by its standard deviation). This was calculated by subtracting the mean plasma Se determined in our pilot study (1.08 $\mu\text{mol/L}$) from the average plasma Se of healthy American children 1.35 ($\mu\text{mol/L}$) and dividing by the standard deviation (0.34). This calculation revealed that 25 subjects are needed per group to obtain 80% power and a significance level of 5%.

All subjects enrolled will be included in the statistical analyses (intent-to treat). A 2-sided statistical test will be used for all analyses and the overall type-I error rate will be controlled at the 5% level. For each dependent variable (plasma selenium, urinary selenium, plasma GPx activity) a 2-way repeated measures ANOVA will be used to examine the difference among groups and over time (primary hypothesis). Tukey's will be utilized as the post-hoc test.

An ordinal logistic regression will be performed to determine the relationship between the incidence of infection (categorized by burn, bloodstream, urinary tract infection, and PNA) and plasma selenium, urinary selenium, plasma GPX, age, initial percent TBSA burned, and treatment group (secondary hypothesis).

Appropriate confounding factors (including but not limited to dietary Se intake, age, sex, race, initial %TBSA, and length of time from burn injury to study enrollment) will be included in the statistical models. All statistics will be completed using SAS software.

VI. Risks and Discomforts

Phlebotomy will be minimal (4 or 8 ml/wk) and will be obtained painlessly through existing catheters or during operative procedures.

Se toxicity is rare. Symptoms include:

- memory loss
- gastrointestinal upset,
- hair loss,
- weakened nails,
- white blotchy nails,
- garlic breath odor,
- metallic taste,
- vomiting,

- sweat
- dermatitis,
- dental defects,
- nervousness,
- mental depression,
- fatigue,
- irritability,
- mild nerve damage,
- Peripheral vascular collapse,
- Internal vascular congestion,
- Hemorrhage,
- Congested and edematus lungs,
- Brick-red color gastric mucosa
- Coma
- Death

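### The infection model puts at least 11 slopes on at most 75 children, so ordinary maximum likelihood pushes any real odds ratio away from 1; inflation of the type I error depends on the test used

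*Combined protocol and SAP*

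**What the plan says.** The statistical paragraphs at the end of section V.D test the secondary hypothesis with a single model: "An ordinal logistic regression will be performed to determine the relationship between the incidence of infection (categorized by burn, bloodstream, urinary tract infection, and PNA"). Its predictors are "plasma selenium, urinary selenium, plasma GPX, age, initial percent TBSA burned, and treatment group (secondary hypothesis").

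The next paragraph applies to all models. It describes the confounders as "including but not limited to dietary Se intake, age, sex, race, initial %TBSA, and length of time from burn injury to study enrollment". Age and initial %TBSA are already in the infection model. Dietary selenium, sex, race and time from burn to enrolment are new. The plan commits to entering such factors; its words are that they "will be included in the statistical models".

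Section IV.B gives the sample: "25 subjects will be in each group (total of 75 subjects"), with three arms ("Patients will be randomly assigned to receive Selenium supplementation (either 2, or 4 ug/kg/day) or a placebo"). The only sample-size calculation concerns plasma selenium. For infection the plan gives no expected count, limit on covariates, selection rule, penalisation or procedure for separation, and it names no test. It does promise that "A 2-sided statistical test will be used for all analyses and the overall type-I error rate will be controlled at the 5% level".

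**The concern.** Maximum-likelihood logistic regression is biased away from the null when few children in the rarer outcome group support each coefficient. Its standard errors and test approximations can also be poor in that range. Here the number of coefficients is large for the sample and has no upper bound.

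This model is the only planned test of the link between selenium and infection, which is also the clinical rationale in section I.C. Any true benefit or harm would be reported as larger than it is. Depending on the test chosen, the 5% error promise might not hold even before multiplicity is counted. The open list also leaves room to choose covariates after the data have been seen.

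**Working it through.** **1. The plan's own figure.** The standardised difference is (1.35 − 1.08)/0.34 = 0.794. Then n = 2 × (1.96 + 0.8416)² / 0.794² = 24.9, so 25 per group. This reproduces, but it sizes the plasma selenium comparison only.

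**2. Slope count.**
- Listed predictors: three biomarkers + age + %TBSA + 2 for three arms = 7 (6 if dose is linear).
- Added confounders: dietary selenium, sex, race (at least 1 slope) and time from burn = at least 4.
- Total: at least 11 (10 with linear dose), or 12 if race has three levels.

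**3. Information per slope, binary any-infection.** The rarer outcome group sets the limit. The documents give no infection proportion for these children, so 25 to 45 infected is an assumption.
- 25 infected: 25/11 = 2.3.
- 37 infected (the most even split): 37/11 = 3.4.
- 45 infected leaves 30 uninfected: 30/11 = 2.7.

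**4. Information per slope, ordinal outcome.** Effective n = n − Σnᵢ³/n², under three assumed frequency patterns with infection-free as the first category.

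| Assumed split (%) | Effective n | Per slope at 11 |
|---|---|---|
| 20 each | 72.0 | 6.5 |
| 50/20/10/10/10 | 64.8 | 5.9 |
| 70/12/8/6/4 | 49.1 | 4.5 |

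**5. Simulated ordinal model, 75 children, 11 slopes, moderately correlated biomarkers.**
- True plasma selenium odds ratio 0.50 per SD (log −0.693): the mean estimate is −0.795 to −0.858, which is 15–24% too far from the null (odds ratio about 0.45 to 0.42).
- True high-dose odds ratio 0.50: the mean is −0.800 (50% infection-free) and −0.843 (70%). The ratios −0.800/−0.693 = 1.15 and −0.843/−0.693 = 1.22 give a bias of 15–22%. With 4 slopes (arm, age, %TBSA) the bias is 6–7%.
- No effect: Wald tests reject 6.4–7.3% and likelihood-ratio tests 7.0–8.8%. The 4-slope Wald test of the high-dose slope rejects 5.3–5.5%.
- High-dose standard error under no effect: mean 0.672 against a true SD of 0.752, and 0.822 against 0.968, so 11–15% too small.
- The 7 listed slopes alone: bias 8–17%, Wald 5.6–7.2%.

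In the high-dose comparison the extra covariates had no effect on infection. The 11- and 4-slope models therefore estimate the same odds ratio, and the gap between them is small-sample bias, not a change of estimand.

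**6. Simulated binary any-infection, 25 per arm, 12 slopes, placebo risk 25–85%.**
- A true odds ratio of 0.50 averages 0.37–0.43. On the log scale, ln 0.43/ln 0.50 = 1.22 and ln 0.37/ln 0.50 = 1.43.
- Firth's penalty returns 0.47–0.50 with 12 slopes and 0.50–0.52 with 4.
- No effect: the 2-df likelihood-ratio test rejects 7.2–8.4%, and up to 10.3% in a separate set of runs. Wald tests range from 1.6% to 6.8% across runs.

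**The case against.** Several parts of the opposing case stand.

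- **The test is not specified.** A reader might infer that the model raises the false-positive rate whatever test is used. The plan names no test, and the Wald test on a binary outcome is near or below 5%. The claim holds for likelihood-ratio tests and, more mildly, for Wald tests on the ordinal outcome.
- **The bias is small relative to the noise.** In binary runs with 12 slopes it is 0.13–0.29 on the log scale against a sampling SD of 0.79–1.30, about one-sixth to under one-quarter of an SD. With only the 7 listed slopes, a true 0.50 averages 0.44–0.46, against 0.47 with 4. Most of the damage comes from the added confounders.
- **The odds ratio is not exaggerated when there is no effect.** It is then centred on 1, but more variable than the model's standard errors suggest.
- **Frequent failure to fit is not established for any infection.** At 25% placebo risk, 0.3–5.5% of fits fail, mostly because an arm has no events. Failure reaches 5–21% only if single infection types with 13–20% incidence are modelled separately.
- **Infection rates are uncertain.** Table 7 cites adult burn trials with about 2 to 4 infections per patient, which hints at a high proportion infected. These are adult episode counts and cannot be converted to a proportion of children. A high rate would not help, because uninfected children then become the scarce group; the binary runs extend to 85% placebo risk for this reason.

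It can also be said that the qualifier at the start of the confounder sentence leaves room for judgement, and that the hypothesis is secondary. Both are true. But the sentence says the factors will be included, and gives no rule for leaving any out.

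**Conclusion.** The concern holds, at moderate size, and should be corrected before analysis. The slope count follows from the text: at least 11 (10 with linear dose) on at most 75 children. Fewer may be usable, because section V.C says urine is not collected from a child who cannot provide it, and a complete-case model would drop such children.

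Fitted by ordinary maximum likelihood, the model overstates non-zero log odds ratios by about 15–25% in the ordinal form with 11 slopes. In a binary form with 12 slopes a true 0.50 becomes about 0.37–0.43. Type I error is about 7–9% for likelihood-ratio tests, 6.4–7.3% for ordinal Wald tests, and near or below nominal for binary Wald tests. An unconditional statement that the 5% level is broken would go beyond what the documents support.

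These sizes rest on assumed infection frequencies, on treatment as a three-level factor and on the simulated covariate structure. The direction of the bias was the same in every scenario run. Whether the four infection types can be ordered at all, and multiplicity across coefficients, are separate matters not counted here.

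**What to change.** - **Treatment effect:** model any infection (yes/no) on arm, age and initial %TBSA (4 slopes) with Firth's penalised likelihood. Base intervals and tests on the profile penalised likelihood. In simulation this combination gave type I error of 4.4–5.4% with no failed fits.
- **Biomarkers:** examine plasma selenium, urinary selenium and GPx each in its own penalised model with a short fixed set: age, %TBSA, dietary selenium and time from burn. Label these exploratory. Randomisation does not balance confounders of a biomarker measured after treatment starts, so dietary selenium and time from burn should stay.
- **Confounder list:** delete the open-ended wording for these models, so that the covariates are fixed before the data are seen.

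The cost is a change of analysis wording. Firth logistic regression is available in SAS, the planned software, and enrolment, dosing and sampling are unaffected. What is lost is a joint model of the three biomarkers and adjustment for sex and race. One model also becomes several, which is why the biomarker results should be labelled exploratory.
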